8.3 Premature termination of the study

8.3.1 Definition of treatment success

The number of successes obtained in this study is based on the target lesions tumour response at 3 months. The following 3 categories of patients will be regarded as treatment success:

1. Patients with complete response on CT (according to RECIST 1.1[38])
2. Patients with partial response on CT (according to RECIST 1.1)
3. Patients with stable disease on CT (according to RECIST 1.1)

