Study endpoints	
Primary endpoint:
 
 • Target lesions tumour response 
Secondary endpoints:
 
 • Overall tumour response • Liver specific progression-free survival post ¹⁶⁶Ho-RE • Non-liver specific progression-free survival • Overall survival • Toxicity • Quality of life • Performance status • ^{99m}Tc-MAA and ¹⁶⁶Ho-PLLA-MS scout and therapy dose SPECT/CTs comparison • ¹⁶⁶Ho-PLLA-MS scout dose and total dose MRI comparison • ¹⁶⁶Ho-PLLA-MS scout dose and total dose PET/CT comparison
Duration of treatment	The study consists of a screening phase of approximately 2 weeks followed by a treatment phase of approximately 2-3 weeks. Patients will be followed until liver specific tumour progression or death has occurred, to a maximum of 12 months.
Methodology	A first cohort of 30 patients will be treated with ¹⁶⁶ Ho-RE. After the first cohort, up to 3 additional cohorts of 6 patients will be treated with ¹⁶⁶ Ho-RE. The total number of patients treated in the HEPAR II trial will therefore be at least 30 and at most 48 patients, depending on the observed number of responses. Early termination at a response interim analysis (after 30, 36 or 42 patients) is determined by pre-defined boundaries on the number of observed responses. The boundary in favour of treatment effect may be crossed before 30 patients are reached, but then the study will continue to at least 30 patients to allow estimation of the key secondary endpoints.
Number of study centers	Single center (UMC Utrecht).
Adverse events	All adverse events will be recorded throughout the study.
Inclusion period	Mar 2012 – Aug 2015
Analysis	
Full analysis will be performed after the last patient's last visit. The primary analysis will be to estimate the target lesions tumour response rate (with 95% confidence interval, adjusted for early stopping if indicated). Secondary analysis will be similar estimations of response rates or estimated survival curves (cumulative incidences). Primary and secondary analyses will be based on the Full Analysis Set; analyses on the Per Protocol Set will also be performed and reported.
 
The study will be monitored with stopping boundaries on the number of observed responses. Early termination may occur as a consequence after 30, 36

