3. STUDY DESIGN

Study type	Interventional
Study design	Interventional, treatment, one group, phase II study with a medical device.
Study start date	Mar 2012
Estimated study completion date	Aug 2015

This phase II study comprises a group of at least 30 and at the most 48 patients suffering from liver metastases of primary cancers of miscellaneous origin. Patients who will be included have hepatic metastases not amenable for surgical resection or further systemic treatment. A liver absorbed dose of 60 Gy will be used in each patient in this study. A radiation dose of 60 Gy equates to 3.8 GBq ^{166}Ho /kg liver tissue.

The primary outcome is target lesions tumour response at three months follow-up. For this study, this is defined as: 1) complete response on CT at 3 months, or 2) partial response on CT at 3 months or 3) stable disease on Computed Tomography (CT) at 3 months (see chapter 8.3.1 Definition of treatment success).

This single arm open label study will have a sequential design as follows. Patients will be followed for target lesions tumour response up to 12 months or less if liver specific tumour progression or death occurs. Interim analyses for tumour response achieved are based on sequential decision boundaries. Stopping boundaries are determined such that an overall one-side alpha of at the most 0.05 is maintained in case the true tumour response is 20% ($p_0 \equiv 20\%$). Early termination at a response interim analysis (after 30, 36 or 42 patients) is determined by pre-defined boundaries on the number of observed responses. The boundary in favour of treatment effect may be reached or crossed before 30 patients are reached, but then the study will continue to at least 30 patients to allow estimation of the key secondary efficacy endpoints. Early stopping for proven efficacy can only occur after the first 30 patients are evaluated. Boundaries for early stopping due to futility, i.e. absence of a relevant effect on tumour response, are also included, and are in effect even before the number of 30 patients is reached. The sequential design with boundaries as given in Table 1 will have a power of 90% to reach a positive tumour response decision in case the true target lesions tumour response is 40% ($p_1 \equiv 40\%$). The exact overall one sided type I error is 4.5% [28].

Table 1 Stopping boundaries for early termination at interim analysis.[28] Stopping is indicated if the observed number of responses is at the boundary or beyond.

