4. STUDY POPULATION

4.1 Inclusion criteria

Patients meeting the following criteria may enter the study:

1. Patients must have given written informed consent.
2. Female or male aged 18 years and over.
3. Diagnosis of metastatic malignancy to the liver and no detectable malignant disease outside the liver or diagnosis of metastatic malignancy to the liver with limited disease outside the liver (i.e. liver-dominant disease) defined as the sum of the diameters of all metastases in the liver to be more than 200% of the sum of the diameters of all soft tissue lesions outside the liver.
4. Patient is not amenable for standard therapies (other than radioembolization) or patient refuses standard therapies for reasons of toxicity
5. Life expectancy of 12 weeks or longer.
6. World Health Organisation (WHO) Performance status 0-2 (see Appendix III).
7. One or more measurable lesions at least 10 mm in the longest diameter by spiral CT according to the Response Evaluation Criteria in Solid Tumours (RECIST) 1.1 criteria.
8. Negative pregnancy test for women of childbearing potential.

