8.2 Withdrawal of individual patients

Patients can abandon the study at any time for any reason if they wish to do so without any consequences for treatment or care. The investigator can decide to withdraw a patient from the study for urgent medical reasons.

Patients will be withdrawn from the study if:

- The investigator considers it in the best interest of the patient that he/she be withdrawn
- The patient withdraws consent
- The patient is unable to comply with protocol procedures

The date and reason for withdrawal must be recorded. If the patient withdraws consent after the therapy dose of ^{166}Ho -PLLA-MS has been administered, the patient will be advised to agree to follow-up safety investigations.

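### Success is scored on the 3-month CT category alone, so lesions held stable by other anticancer therapy started after the therapy dose count as device successes

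*Protocol*

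**What the plan says.** Section 8.3.1 states "The following 3 categories of patients will be regarded as treatment success" and lists complete response, partial response and stable disease on CT under RECIST 1.1. Sections 3 and 8.1.1 give the same definition, at 3 months. Under section 8.3.2 a patient is a failure if the 3-month assessment shows progression or if death occurs within that period. None of these sections mentions other anticancer therapy.

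Other places bear on the point:

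- **Eligibility (4.1, no. 4).** A patient may enter who has no standard option, or where the "patient refuses standard therapies for reasons of toxicity". No. 3 admits limited disease outside the liver.
- **Follow-up (Summary, Duration of treatment).** "Patients will be followed until liver specific tumour progression or death has occurred, to a maximum of 12 months". Extrahepatic progression and the start of another therapy do not end it.
- **Withdrawal (8.2).** The reasons are the patient's best interest in the investigator's view, withdrawn consent, and "The patient is unable to comply with protocol procedures".
- **Analysis sets (10).** The PPS, on which the response decision is primarily based, requires compliance with the protocol to at least 3 months. In the FAS, failure is imputed for patients who did not reach 3 months.
- **Decision rule (3).** The boundaries are set so that "an overall one-side alpha of at the most 0.05 is maintained in case the true tumour response is 20" per cent.

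**The concern.** The trial has one arm, and stable disease is enough for success. If another treatment started between the therapy dose and the 3-month CT holds the liver lesions stable, the plan has no means of separating that effect from the device effect. An added anticancer therapy would be expected to turn some failures into successes and not the reverse, so the error runs in one direction.

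The success count drives the Table 1 decision. Section 8.4 says the main objective is to decide whether to proceed to a phase III trial, and section 12.8 says the data will support a CE marking application. Liver-specific progression-free survival (8.1.2) has the same gap over up to 12 months, because its event is liver progression and no rule covers therapy started in between.

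**Working it through.** **Step 1: look for a rule.** Each place where one could sit was checked.

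| Place in the protocol | What it covers | Rule on therapy after the dose? |
|---|---|---|
| 4.2, nos. 2, 3 and 16 | Radiotherapy, chemotherapy and investigational agents before study therapy | No |
| 5.6, 5.7 | Prophylactic and supportive medication | No |
| 8.2 | Withdrawal reasons | Not named |
| 8.2.1 | Replacement of patients not evaluable for response | Not named |
| 8.3.1, 8.3.2 | Success and failure | No |
| 10 (PPS) | Compliance to 3 months | Not named; no section forbids such therapy, so starting it is not defined non-compliance |
| 10 (FAS) | Failure imputed if 3 months was not reached | Does not reach a patient scanned at 3 months |
| 11.2.1 | Consent covers obtaining data on additional treatment | Data foreseen, no analysis rule |

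A patient who starts another therapy at, say, week 6 and has stable target lesions and no new lesions at 3 months is therefore a success in both sets.

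**Step 2: reproduce the plan's figures.** Inputs from section 3 and Table 1: p0 = 0.20, p1 = 0.40, looks at n = 30, 36, 42 and 48, lower/upper boundaries 5/11, 6/13, 7/14 and 15/16, and "Stopping is indicated if the observed number of responses is at the boundary or beyond". Let f_n(x) be the probability of x successes after n patients with no earlier stop. Between looks f is updated by adding independent Bernoulli(p) outcomes; at each look the mass at or beyond either boundary is removed. Then

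P(positive) = Σ over looks of Σ_{x ≥ upper} f_n(x).

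- p = 0.20: 0.0256 + 0.0048 + 0.0113 + 0.0035 = 0.0452. The protocol says "The exact overall one sided type I error is 4.5" per cent.
- p = 0.40: 0.7085 + 0.0694 + 0.0899 + 0.0301 = 0.8979. The protocol says the design "will have a power of 90% to reach a positive tumour response decision in case the true target lesions tumour response is 40" per cent.

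Both figures reproduce. Treating the lower boundaries as non-binding gives 0.0453 and 0.898. Futility stopping before 30 patients could not be modelled, because Table 1 gives no boundary for it.

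**Step 3: let the counted rate exceed the device rate.** Suppose the device alone gives 20%. A share s of would-be failures starts another therapy before the 3-month CT, and a fraction c of those is then stable or better:

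counted rate = 0.20 + 0.80 × s × c.

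The protocol gives neither s nor c; both are assumptions.

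| s | c | Counted rate | P(positive) |
|---|---|---|---|
| 0 | – | 0.200 | 4.5% |
| 5% | 20% | 0.208 | 6.0% |
| 10% | 20% | 0.216 | 7.7% |
| 5% | 50% | 0.220 | 8.7% |
| 10% | 30% | 0.224 | 9.8% |
| 10% | 50% | 0.240 | 15.0% |

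At a counted rate of 0.21, P(positive) is 6.4%, already above the 0.05 ceiling. One percentage point is 0.01 × 48 = 0.48 of a patient at the maximum sample size.

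**Step 4: price the remedy.** If starting other therapy is scored as not a success, and a share s of true device successes also starts it, the counted rate is p × (1 − s).

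| s among true successes | Rate under p0 | Type I error | Rate under p1 | Power |
|---|---|---|---|---|
| 0 | 0.20 | 4.5% | 0.40 | 89.8% |
| 5% | 0.19 | 3.1% | 0.38 | 84.1% |
| 10% | 0.18 | 2.1% | 0.36 | 76.5% |

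**The case against.** **The protocol is silent, and a statistical analysis plan may settle it.** A reader might infer that the protocol expressly counts these patients as successes. It does not; the result follows from applying 8.3.1, 8.3.2 and 10 as written. But those sections fix success and failure, and an analysis plan should implement that definition, not add a condition to it. The argument has more force for liver-specific progression-free survival, where handling of new therapy is ordinary analysis-plan detail, so only a sensitivity analysis is asked for there.

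**Such patients might leave the PPS.** The compliance wording could be read that way, and the investigator can withdraw a patient on best-interest grounds. Both routes are discretionary. A patient who left would be replaced under 8.2.1 in the response cohort, not counted as a failure there. One who stays on study and is scanned at 3 months remains a success in the FAS.

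**It will be uncommon.** This largely stands. A reader might infer from the refusal route in 4.1 that later therapy is likely. The documents do not support that: the Summary, section 3 and section 11.2 describe patients mainly without standard options; Table 2 schedules no response imaging between treatment and 3 months, so earlier detection needs a discretionary scan under 8.1.2; and 8.1.1 already scores new lesions as progression. No frequency can be derived.

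**Scoring such patients as failures is one choice among several.** It fails a patient whose liver lesions truly responded but who started systemic therapy for disease elsewhere. That is a fair criticism, and the reason for reporting the CT-only count beside it.

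**Conclusion.** The gap is real and sits in the definition of success. Followed as written, the protocol credits the device with stabilisation produced by another therapy started before the 3-month CT, in both analysis sets, with no control arm to correct for it.

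The design arithmetic is sound, and the 4.5% should not be read as miscalculated: it holds when the counted rate under an ineffective device is 20%. Nor are the higher figures estimates of this trial's actual error rate. They show sensitivity: 6.4%, 8.7% and 15.0% at counted rates of 21%, 22% and 24%. What the documents support is the direction of the error and the thin margin, since an excess of one percentage point takes the rate above 0.05. The calculation assumes independent patients, Table 1 applied exactly, and added therapy that never turns a success into a failure. The protocol should be changed because the repair is cheap and is best fixed before results are seen.

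**What to change.** 1. In 8.3.1 and 8.3.2, state that a patient who starts other systemic anticancer or liver-directed therapy between the therapy dose and the 3-month CT is scored as not a success in the boundary decision. This extends the conservative imputation that section 10 already uses for the FAS.
2. In 8.2.1 and 10, state that such a patient stays in the PPS and the FAS and is not replaced.
3. Report the success count scored by CT category alone as a sensitivity analysis.
4. For liver-specific progression-free survival, add a sensitivity analysis with the start of new anticancer therapy as an event.
5. Record in the E-CRF the start date of any such therapy, including liver-directed procedures. The existing concomitant-medication record is not sufficient: Table 2 and section 5.2.4 schedule none at week 1, and a medication record may not date procedures.

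The cost is a few protocol sentences, one E-CRF item and two sensitivity analyses. The reported success rate may be lower. Power falls below the stated 90% if true responders also start other therapy: to 84.1% if 5% do and 76.5% if 10% do. If such therapy is rare, the loss is small.

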8.3.2 Determination of ineffective therapy

Therapy for an individual patient is regarded ineffective if target lesions tumour response assessment at 3 months indicates progressive disease according to RECIST 1.1 or if death occurs within this period.

Early termination of the study for lack of efficacy (futility) will be guided by the lower group sequential boundary on the number of patients with treatment success (see 8.3.1). Advice to stop early will be given by the Independent Data Monitoring Committee, that may include other considerations (safety) as well.

8.4 Independent Data Monitoring Committee (IDMC)

An IDMC is established. The IDMC is an independent group comprising internal members (from within the UMCU) and external members. This phase II study is open label and patients are individually closely monitored for safety, as was done in the HEPAR I study. The main objective is to decide whether or not to embark on a larger phase III trial. Hence it was considered adequate to establish an IDMC with both (independent) internal UMCU members as well as an external member. In case of a future phase III trial, a fully external IDMC is strongly recommended. The IDMC includes the following members:

- Dr. [name], Meander Medical Center Amersfoort; nuclear medicine physician
- Dr. [name], University Medical Center Utrecht; gastro-enterologist
- Dr. [name], Albert Schweitzer ziekenhuis; interventional radiologist
- Dr. [name], Julius Center Health Sciences and Primary Care Utrecht; biostatistician

The IDMC will analyse preliminary study results on tumour response after the first 30 patients who are amenable for tumour response assessment at 3 months (i.e. PPS), and every 6 patients who are amenable for tumour response assessment at 3 months thereafter (see Table 5). Waiting for the three-month follow-up of all 30/36/42/48 patients is only required if, based on the available follow-up in the other patients, it remains uncertain whether the stopping boundaries will be reached.

The IDMC analyse preliminary study results on safety as well (see Table 5). In contrast to the tumour response analyses, the safety analyses will include all patients that received treatment within a time span of 3 months (regardless of their availability for tumour response assessment, i.e. FAS), and therefore, these reviews may not run in sync with the IDMC tumour response analyses. Patient inclusion and treatment may continue during IDMC safety analyses. In its safety analyses, the IDMC will consider specifically the reasons and potential consequences on treatment benefit of the patients that discontinued before the 3 months assessment. The IDMC will receive reports on a regular basis on all SAEs reported for this trial and a complete summary safety report for each safety analysis. The IDMC will work according to the IDMC charter (see Appendix VIII) Recruitment will not be interrupted unless otherwise requested by the IDMC Chairman.

The responsibilities of the IDMC include:

- To safeguard the safety of current and future participating patients
- To safeguard the continued scientific merit of the trial
- To evaluate whether the efficacy data comply with the stopping criteria, and advice accordingly taking all data into account
- To make recommendations for changes in study processes where appropriate
- To advice on continuation of the study

The IDMC will report to the Principal Investigator (on behalf of the sponsor), who is responsible of communicating to others (e.g. the METC) as appropriate or required by regulation.

Assessing safety signals for concern in this population is a complex matter, taking into account the adverse events caused by the disease as well as weighing safety versus the potential benefit in this population with poor prognosis. This is further compounded by the lack of comparative group in this design. Treatment related adverse events and serious adverse events in this heavily pretreated and advanced patient population are difficult to distinguish from adverse events caused by the underlying disease and comorbidities. Life-threatening toxicity should always be carefully analysed and weighed against treatment effect, but given the population, grade 3-4 toxicities will occur in a substantial proportion of study patients. Liver enzyme toxicity, for instance, occurs frequently in this patient category, but is only considered life-threatening if the metabolic function and/or the productive function of the liver are compromised. Therefore, only bilirubin grade 3-4 and/or factor V grade 3-4 toxicity occurring in >30% of the study population, must be regarded as a clear sign that the toxicity of ¹⁶⁶Ho-RE may outweigh the potential palliative benefits. This guideline assumes analysis of at least 12 patients in order to base this conclusion on sufficient data. All other CTCAE grade 3-4 events, excluding liver enzyme toxicity, may occur in up to 50% of the study population, this also implies analysis of at least twelve patients. Grade 3-4 events which can clearly be attributed to disease or comorbidity, are excluded from this guidance.

Table 5. IDMC review scheme

IDMC tumour response analysis*	Patient series	IDMC safety analysis**
No. 1	1-30	Every 3 months
No. 2	30-36	
No. 3	36-42	
No. 4	42-48	

* IDMC tumour response analyses will be held after the first 30 patients and every 6 patients thereafter. Primarily, patients who are available for tumour response assessment 3 months post treatment are evaluated (PPS). FAS data will be analysed during IDMC reviews of safety

** IDMC safety analyses will be held every 3 months after treatment of the first patient. All patients that received ¹⁶⁶Ho-RE will be evaluated (FAS). Safety analysis will at least be held after treatment of 30 patients.

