	Coagulation profile	Reagent-independent prothrombin ratio prothrombin time/ partial thromboplastin time (PT/PTT). If PT and/or PTT are out of range, Thrombin time (TT) will be automatically measured. Activated partial thromboplastin time (APTT).
	Serum chemistry	Creatinine, total bilirubin, alkaline phosphatase, SGPT/ALT, SGOT/AST, γ GT, glucose, chloride, calcium, potassium, sodium, total protein, albumin, bicarbonate, urea, magnesium, phosphorus, ammonia, LDH, CRP and relevant tumour markers.
Total: 10 ml		
Type B (blood)	Hematology	Leukocytes, erythrocytes, hemoglobin (Hb), hematocrit (HCT), mean corpuscular volume (MCV), mean corpuscular hemoglobin (MCH), mean corpuscular hemoglobin concentration (MCHC), differential leukocyte count (neutrophils, lymphocytes, monocytes, eosinophils, basophils) and platelet count.
	Serum chemistry	Creatinine, total bilirubin, alkaline phosphatase, SGPT/ALT, SGOT/AST, γ GT, glucose, albumin, ammonia, lactate dehydrogenase (LDH) and C-reactive protein (CRP).
	Total: 4 ml	
Type C (blood and urine)	Holmium content	Holmium content.
	Total blood: 7 ml	

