5.4 Laboratory examinations

Blood samples for safety parameters will be taken using an indwelling canula or by single vein puncture. During the follow-up visits with the investigator, blood samples for safety parameters will be drawn by a research nurse and delivered to the Laboratory of Clinical Chemistry and Haematology (see Table 3).

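### The IDMC's >30% liver toxicity guideline counts grade 3-4 bilirubin and/or factor V, but no scheduled blood panel measures factor V

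*Protocol*

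**What the plan says.** Section 8.4 explains that liver enzyme rises are frequent in these patients, and that such toxicity "is only considered life-threatening if the metabolic function and/or the productive function of the liver are compromised". From this it derives its stricter numerical safety guideline: "only bilirubin grade 3-4 and/or factor V grade 3-4 toxicity occurring in >30% of the study population" is to be taken as a clear indication that toxicity may outweigh the palliative benefit. At least 12 patients must have been analysed. Other grade 3-4 events, apart from liver enzymes, are allowed in up to 50% of patients.

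Section 5.4 refers to Table 3 for the safety bloods taken at follow-up visits. Table 3 has three panels:

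- **Type A:** haematology, a coagulation profile (PT/PTT, reflex thrombin time, APTT) and serum chemistry including total bilirubin.
- **Type B:** haematology and a shorter chemistry list including total bilirubin, albumin and ammonia, with no clotting test.
- **Type C:** holmium content only.

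Table 2 and section 5.2 place type B at weeks 3, 6 and 9, and type A at months 3, 6, 9 and 12 as well as at screening, pre-treatment and treatment. On the length of follow-up, the Summary says: "Patients will be followed until liver specific tumour progression or death has occurred, to a maximum of 12 months".

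**The concern.** The guideline joins two markers with and/or, so a patient with grade 3-4 toxicity on either should count. Only one of them is scheduled. In the text at hand, factor V appears in section 8.4 and nowhere else.

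A statement that the 30% level was not exceeded would then rest on bilirubin alone. A patient with grade 3-4 factor V but not bilirubin toxicity would be found only if someone happened to order the test. Section 9.5 allows extra tests to follow up an individual adverse event, but selective testing does not give a proportion of all treated patients.

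Liver function is a central hazard here. According to section 6.3, the 80 Gy cohort of the phase I trial was stopped for dose-limiting toxicity, and radiation-induced liver disease was suspected in one patient.

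**Working it through.** **1. Schedule against guideline.** Follow-up draws after treatment, from Tables 2 and 3:

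| Marker | Weeks 3, 6, 9 (type B) | Months 3, 6, 9, 12 (type A) | Total of 7 | Up to month 3, of 4 |
|---|---|---|---|---|
| Total bilirubin | 3 | 4 | 7 | 4 |
| PT/PTT, APTT | 0 | 4 | 4 | 1 |
| Factor V | 0 | 0 | 0 | 0 |

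Screening and pre-treatment draws are left out because they cannot show treatment toxicity. The treatment-visit type A draw is left out because its timing relative to the dose is not stated. If it falls after the dose, bilirubin becomes 8 of 8 and the clotting tests 5 of 8 (2 of 5 up to month 3); factor V stays at zero. The last column is all the follow-up of a patient whose liver disease has progressed by month 3.

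**2. Blood volume.** Type A is drawn seven times at 10 ml and type B three times at 4 ml. Type C is drawn four times at 7 ml, if 7 ml is per time point. The total is 70 + 12 + 28 = 110 ml, the figure in section 11.3.2. The listed panels account for the whole budget, which suggests that no separate factor V sample was planned. It does not exclude an extra assay on an existing tube.

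**3. What exceeding 30% means.** The smallest counts above 30% are:

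- n = 12: 4 patients (33.3%; 3/12 is 25%)
- n = 30: 10 patients (33.3%; 9/30 is exactly 30%)
- n = 48: 15 patients (31.25%; 14/48 is 29.2%)

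**4. Effect of the missing marker.** The protocol gives no grade 3-4 rate for bilirubin or factor V, so every rate below is an assumption. Let b be the proportion with grade 3-4 bilirubin and f the proportion with grade 3-4 factor V but not bilirubin. The guideline as written counts patients at rate p = b + f; the schedule shows only b. The chance of exceeding 30% is the exact binomial tail P(X ≥ r | n, p), with r from step 3.

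For n = 30, r = 10:

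| b | Bilirubin only (f unseen, or f = 0) | f = 5% seen | f = 10% seen | f = 15% seen |
|---|---|---|---|---|
| 5% | <0.001 | <0.001 | 0.010 | 0.061 |
| 10% | <0.001 | 0.010 | 0.061 | 0.197 |
| 15% | 0.010 | 0.061 | 0.197 | 0.411 |
| 20% | 0.061 | 0.197 | 0.411 | 0.642 |
| 25% | 0.197 | 0.411 | 0.642 | 0.824 |

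For small f at n = 30, b = 10% gives 0.0005 on bilirubin alone, and 0.001 or 0.002 with f = 1% or 2%. At b = 25% the figures are 0.197, then 0.235 or 0.276.

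Other sample sizes, bilirubin only and then f = 5/10/15%:

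- n = 12, b = 10%: 0.026, then 0.092/0.205/0.351
- n = 12, b = 25%: 0.351, then 0.507/0.653/0.775
- n = 48, b = 10%: <0.001, then 0.003/0.044/0.200
- n = 48, b = 25%: 0.200, then 0.479/0.754/0.919

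**The case against.** The strongest reply is that this is guidance and not a stopping rule, so little follows from the gap. No automatic stop is attached, bilirubin alone can trigger it, and the efficacy boundaries, type I error and power do not depend on it. The IDMC reviews safety every three months on all treated patients, receives reports on all SAEs and "a complete summary safety report for each safety analysis", and may recommend changes to study processes, including this assay. Albumin and ammonia are in panels A and B, and clotting times in panel A, so synthetic function is not wholly unobserved. This stands, and it limits the severity. It does not supply the missing count: a summary cannot contain results that were never collected, and the protocol names none of these tests as a substitute for factor V. A grade 3-4 clotting abnormality from panel A would come under the looser 50% guideline.

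The second reply is that the probabilities rest on invented rates. That also stands. The large differences need a bilirubin rate close to 30% together with a sizeable isolated factor V rate, and nothing in the protocol supports that pairing. The table shows how sensitive the count is and does not estimate harm. The inconsistency itself depends on none of these rates.

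Third, the IDMC charter (Appendix VIII), the laboratory appendix (Appendix V) and the CTCAE appendix (Appendix II) are not at hand and may mention factor V. A list of normal values or grades would not schedule a test, however. The charter might provide for one, but the protocol's own schedule would still need to match.

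**Conclusion.** The concern holds. Section 8.4 sets a safety guideline on two markers, and the protocol's schedule collects one of them. Factor V is measured at 0 of up to 7 follow-up draws after treatment, so the guideline cannot be applied as written.

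The practical loss ranges from nothing, if factor V toxicity never occurs without high bilirubin, through almost nothing when bilirubin toxicity is rare, to large when the bilirubin rate lies just under 30% and isolated factor V toxicity is common. The documents do not show which case applies. Because the guideline is advisory and the IDMC has other information, this is a point that should be fixed and not a threat to the trial. The conclusion assumes that the appendices not at hand do not schedule the assay.

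**What to change.** Add factor V to panels A and B in Table 3, at the draws already planned. State in section 8.4 which values count as grade 3-4, or point to the definition in Appendix II if there is one. If the investigators prefer a routine test, replace factor V in section 8.4 with PT/INR, give its cut-off, and add it to panel B so that weeks 3, 6 and 9 are covered. If the charter or Appendix V already provides for factor V, carry it into Table 3.

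The cost is one assay per existing draw and a line each in Table 3 and section 8.4, with no new visit or puncture. If panel B needs a separate clotting tube (assumed 2-3 ml at three visits, so 6-9 ml), the 110 ml in section 11.3.2 becomes about 116-119 ml.
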